10.4.10 TABULATION OF INDIVIDUAL RESPONSE DATA

Individual participant data will be listed by time point.

10.4.11 EXPLORATORY ANALYSES

Not applicable.

10.5 SAMPLE SIZE

The PI has used G*Power 3.10.10 software⁴ to generate *a priori* minimal sample size calculations for the primary study endpoint: changes in *gross elasticity* (GE) repeated measure face measurement in a sample of consented eligible women at three time points: a) prior to RF/PEMF, b) at time of RF/PEMF completion, and c) three months after treatment completion.

These calculations indicate that a minimal sample size of approximately **45** patients would easily afford at least a 0.804784 $1 - \beta$ level of statistical power to detect statistically significant RF/PEMF sample subgroup measurement differences observing a coefficient Alpha of 0.05 two-tailed level of significance. This sample size is based on both a conservative 0.3 (i.e., *Medium*) Effect Size for RF/PEMF treatment and pre-post procedure Cutometer[®] face gross elasticity measurement differences reported in Krueger, et. al (2011).⁵

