Summary:	This study is an open-label, baseline-controlled, single-center study to measure the change in skin elasticity after combined radio frequency (RF) and pulsed electromagnetic field (PEMF) treatment. Forty-five adult females will undergo weekly treatments over a period of 8 weeks. Skin elasticity will be measured by a Cutometer® prior to beginning treatment, week 7 and 3 months after completion of treatment. Photographs will be taken prior to treatment, at week 4, week 7 and 3 months after completion of treatment. Patient discomfort/pain and satisfaction questionnaires will be completed before, during and after treatment.
Objectives:	The objective is to determine the quantitative change in elasticity of facial skin in subjects who have undergone treatment with combined RF and PEMF.
Endpoint	
Primary endpoint:
 
Quantitatively and objectively measure the change in facial skin elasticity following combined radio frequency and electromagnetic treatment. 
Secondary endpoints:
 
Improvement in facial skin laxity at 7 and 20 weeks post-intervention compared to baseline as assessed by blinded evaluators by photographic assessment utilizing the Fitzpatrick Wrinkle and Elastosis Scale (FWES) scale.Improvement in subject appearance at 7 and 20 weeks post-intervention compared to baseline as assessed by the subject utilizing the Global Aesthetic Improvement Scale (GAIS)Improvement in subject satisfaction with facial skin laxity at 4, 7 and 20 weeks post-intervention compared to baseline as measured by the 5-point Likert Subject Satisfaction questionnaire.
Population:	The study will enroll approximately 45 healthy adult females desiring improvement in facial skin elasticity and tightness.
Phase:	Post-approval
Number of Sites enrolling participants:	One site
Description of Study Agent:	Venus Versa is an FDA approved aesthetic device. The Diamondpolar applicator combining multi-polar RF and PEMF energies will be used in this study. It is approved for non-invasive skin tightening of the face in skin types I - IV.
Study Duration:	8 months

Participant Duration: 5 months

SCHEMATIC OF STUDY DESIGN

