4.2.1 PRIMARY ENDPOINT

As skin ages, collagen can become disorganized, causing changes in both the mechanical property of the skin and skin appearance. The change in gross elasticity ($R2$ or Ua/Uf which is a ratio of maximum recovery (Ua) and skin distensibility (Uf)) as measured by a Cutometer® has been found to be one of the most suitable parameters to represent the influence of aging on skin mechanical properties.¹ This is expressed as a percentage, the closer the value is to 1 (100%), the more elastic the skin. Thus, the primary endpoint will be the change in gross elasticity after treatment with combined RF and PEMF. The gross elasticity of facial skin will be measured prior to the start of the treatment regimen (baseline), and 20 weeks after completion of the treatment regimen.

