10.2 STATISTICAL HYPOTHESES

Statistical null hypothesis for primary endpoint: there will be no statistical change in gross elasticity as measured by the Cutometer[®] after treatment with combined RF/PEMF compared to before treatment.

Statistical null hypothesis for secondary endpoint #1: there will be no statistical change in the FWES as rated by blinded clinicians after treatment with combined RF/PEMF compared to before treatment.

Statistical null hypothesis for secondary endpoint #2: there will be no statistical change in the GAIS as rated by the subjects after treatment with combined RF/PEMF compared to before treatment.

Statistical null hypothesis for secondary endpoint #3: there will be no statistical change in the subject satisfaction score after treatment with combined RF/PEMF compared to before treatment.

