10.4 DESCRIPTION OF STATISTICAL METHODS

10.4.1 GENERAL APPROACH

After data set compilation and cleaning, a series of descriptive statistics will first be generated to examine the data set for distributional/potential missing data patterns and sample characteristics. The study team will conduct a series of pooled time series analyses with generalized estimating equations regression (GEE) models.³ These types of non-parametric (i.e., not based on normal distribution assumptions) predictive modeling procedures are capable of using both robust and standard estimating functions to more fully evaluate the influence RF/PEMF treatments and other factors/covariates on serial face gross elasticity measurements. These types of procedures will also enable the study team to examine the potential effects of both *within group* (e.g., face gross elasticity measurements for Patient X at three measurement points) and *between group* (e.g., face gross elasticity measurement changes of younger women versus older women) model variables. A *P*-value of <0.05 will be considered statistically significant.

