10.4.2 ANALYSIS OF THE PRIMARY EFFICACY ENDPOINT(S)

Gross elasticity as measured by the Cutometer® is a ratio expressed as a percentage. Baseline and post-treatment measurements will be taken and analyzed using analysis of variance (ANOVA).

Results will be reported as baseline means with standard deviation, post-treatment means with standard deviation, and individual change for each subject.

Subjects with missing data, non-adherence, or lost to follow-up will not be included in the final analysis dataset.

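### Section 10.5 gives power for gross elasticity at three visits, but 4.2.1 defines the primary endpoint as a change between two, and no section says which test decides

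*Combined protocol and SAP*

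**What the plan says.** Section 10.5 presents "minimal sample size calculations for the primary study endpoint" and describes that endpoint as a repeated measure of gross elasticity "at three time points: a) prior to RF/PEMF, b) at time of RF/PEMF completion, and c) three months after treatment completion". It says that about 45 "patients would easily afford at least a 0.804784" level of power, at a two-tailed alpha of 0.05 and an effect size of 0.3.

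Section 4.2.1 defines the primary endpoint as the change in gross elasticity (R2), which "will be measured prior to the start of the treatment regimen (baseline), and 20 weeks after completion of the treatment regimen". It mentions no intermediate reading.

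The other sections leave the choice open:
- The protocol summary schedules the Cutometer "prior to beginning treatment, week 7 and 3 months after completion of treatment". Its primary endpoint names no visit.
- Section 10.2 states the null hypothesis that "there will be no statistical change in gross elasticity as measured by the Cutometer", after treatment compared with before, again without a visit.
- Section 10.4.1 plans GEE models and gives as an example "face gross elasticity measurements for Patient X at three measurement points".
- Section 10.4.2 applies ANOVA to baseline and post-treatment readings without saying which post-treatment reading or readings.
- Section 7.3.4 places Visit 9 twelve weeks (± 2 weeks) after the last treatment.

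**The concern.** The two descriptions lead to different tests. A three-visit comparison asks whether mean elasticity differs at any of the visits. The 4.2.1 endpoint asks whether the final reading differs from baseline. Suppose elasticity rises by week 7 and is back at baseline by the final visit. The three-visit test can then succeed although the change defined as primary is zero.

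This is a single-arm, open-label study, so a contrast fixed in advance is one of its few protections. Section 10.1 says the analysis plan will be finalised only once data collection is complete, which leaves room to settle the deciding test late. It is also unclear whether the stated power supports the endpoint that the protocol defines.

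**Working it through.** **1. The plan's own figure.** Inputs from 10.5 are n = 45, effect size 0.3, two-tailed alpha 0.05 and three time points. Not stated are the G*Power test family, the effect-size metric, the number of groups, the correlation between visits and any sphericity correction. For a one-group within-subject F test with Cohen's f = 0.3,

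λ = f² × n × 3 / (1 − ρ) = 0.09 × 45 × 3 / (1 − ρ) = 12.15 / (1 − ρ), with df 2 and 88.

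Power is 0.876, 0.965 and 0.994 at ρ = 0, 0.3 and 0.5. Other settings give other values: 0.797 with a sphericity factor of 0.75 at ρ = 0, and 0.8055 for a between-group test with four groups at ρ = 0. The printed 0.804784 cannot be reproduced from the printed inputs. That does not show it to be wrong.

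**2. Timing of the final reading.** The last treatment is at week 7.
- Section 4.2.1: 20 weeks after completion, 7 + 20 = about week 27.
- Section 7.3.4: 12 ± 2 weeks after the last treatment, 7 + 10 to 7 + 14 = weeks 17 to 21.
- Section 10.5: three months after completion, in line with 7.3.4 but not with 4.2.1.

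**3. Illustration: what a three-visit power of 0.804784 would imply for two visits.** Assume a one-group omnibus F test with equal variances σ² and equal correlations ρ. Power 0.804784 on df 2 and 88 needs λ = 10.085. For visit means (0, a, b), let SS be the sum of squared deviations of the three means. Then

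λ = n × SS / [σ²(1 − ρ)], and for the paired baseline-to-final t test (df 44), ncp² = n × b² / [2σ²(1 − ρ)] = λ × (b²/2) / SS.

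Both σ and ρ cancel.

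| Visit means | SS | (b²/2)/SS | ncp² | Two-visit power |
|---|---|---|---|---|
| Steady rise (0, 0.5, 1) | 0.500 | 1.000 | 10.085 | 0.87 |
| Week 7 gain kept (0, 1, 1) | 0.667 | 0.750 | 7.564 | 0.77 |
| A quarter lost (0, 1, 0.75) | 0.542 | 0.519 | 5.236 | 0.61 |
| Half lost (0, 1, 0.5) | 0.500 | 0.250 | 2.521 | 0.34 |

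With means (0, 1, 0), ncp² is 0. The three-visit test still rejects in about 80% of studies, while the two-visit test rejects at its 5% error rate.

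Unequal correlations move these values either way. Three-visit power was held near 0.80 by simulation under two patterns: 0.8 between adjacent visits with 0.5 baseline-to-final, and 0.3 with 0.6. Two-visit power for a kept gain then ran from about 0.6 to about 0.9.

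**4. The effect size of 0.3 read directly for two visits, n = 45, two-sided 5%.**
- As a multiple of the SD of change: ncp = 0.3 × √45 = 2.01, power 0.50.
- As Cohen's f for two visits: f = δ/(2σ), so δ = 0.6σ, and the change in SDs of change is 0.6/√[2(1 − ρ)] = 0.424, 0.507 and 0.600 at ρ = 0, 0.3 and 0.5. Power is 0.795, 0.914 and 0.976.

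**5. What 45 completers can detect.** A paired t test on df 44 reaches 80% power at a mean change of 0.427, about 0.43, SD of the within-subject change. This does not depend on the unstated metric.

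**The case against.** The strongest reply is that the plan already leans towards a before-after comparison. Section 10.2 compares after treatment with before. Section 10.4.2 reports baseline means, post-treatment means and each subject's change, and 10.4.10 lists individual data by time point, so a return to baseline would be visible. This is fair as to reporting. It does not settle the test, because the post-treatment visit is never named and 10.5 counts three visits for the same endpoint.

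A second reply is that 45 may serve 4.2.1 well: with 0.3 as Cohen's f for two visits, power is 0.795 or more at any non-negative correlation. This also stands, so the mismatch does not show that the study is underpowered.

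A third is that 10.5 may not describe a one-group omnibus test at all. It speaks of differences between sample subgroups, and 10.4.1 mentions comparing younger with older women. That is correct, and it is why step 3 of the working is only an illustration.

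A reader might also infer a false-positive rate of about 10%, from counting success on any one of the three-visit test, the week 7 change and the final change. That calculation needs a standalone week 7 test as a route to success, and no section proposes one.

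**Conclusion.** The concern holds as an inconsistency in the primary endpoint and should be fixed. The visit sets in 4.2.1 and 10.5 differ, the final reading is placed about six to ten weeks apart (week 27 against weeks 17 to 21), and no section names the deciding test. A three-visit result can therefore be positive when the change defined in 4.2.1 is zero. That consequence needs no assumption about the effect size.

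The size of any power shortfall cannot be determined. The values 0.87, 0.77, 0.61 and 0.34 assume that 0.804784 is a one-group three-visit omnibus power with equal variances and correlations, which 10.5 does not state. The direct two-visit readings run from 0.50 to 0.976, so the missing metric and correlation matter at least as much as the number of visits.

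Four stronger readings are tempting but not supported:
- That 0.804784 is an arithmetic error. Too few inputs are printed to say so.
- That true two-visit power lies between 0.05 and 0.87. The upper end fails under unequal correlations, and the lower end is only alpha at zero effect.
- That the stated power carries over only if elasticity keeps rising after treatment ends. With unequal correlations, a gain that is merely kept can exceed 0.80.
- That more than 45 completers are needed. The plan gives no expected change or SD of change from which to judge that.

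**What to change.** Reconcile the time of the final reading across 4.2.1, 7.3.4 and 10.5.

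In 10.4.2, state: *The primary test is the single contrast Visit 9 minus baseline in R2, two-sided 5%; the week 7 change and the three-visit comparison are secondary and cannot establish the primary endpoint.* Match 4.2.1 and 10.2 to this wording.

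In 10.5, replace 0.804784 with the power for that contrast: *45 completers give 80% power for a mean change in R2 of 0.43 SD of the within-subject change.* State the assumed SD of change, and if 0.3 is kept, state its metric and the correlation used. The 0.43 SD shows what 45 completers can detect, not that a change of that size is likely.

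Two smaller edits belong in the same revision. Clarify the reference in 10.5 to sample subgroups rather than simply deleting it, because it may be the only clue to the test that was run. Reconcile the pre-post Cutometer differences that 10.5 attributes to a published source with 2.1 and 2.2, which say that no earlier study used objective parameters or quantified the improvement.

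The cost is text edits to a few short sections before the data are analysed. The sponsor must commit to an SD of change and gives up claiming the primary endpoint on week 7 alone.

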10.6 MEASURES TO MINIMIZE BIAS

10.6.1 ENROLLMENT/ RANDOMIZATION/ MASKING PROCEDURES

At screening, once a subject has signed the informed consent, and inclusion/exclusion criteria has been met, a subject number will be assigned. The subject number will consist of a two-digit code corresponding to the site and a two-digit subject code in numerical sequence. (Example: 10-05 corresponds to site #10, subject #5.)

Due to the nature of the treatment, it is not possible to blind subjects.

Photographic imaging provided to the raters will not contain any participant identifying information or dates. The physician raters will be blinded to which stage of treatment (if any) completed by the subject in the photograph.

10.6.2 EVALUATION OF SUCCESS OF BLINDING

Not applicable.

10.6.3 BREAKING THE STUDY BLIND/PARTICIPANT CODE

There are no instances in which the blind will need to be broken for the physician raters.

11 SOURCE DOCUMENTS AND ACCESS TO SOURCE DATA/DOCUMENTS

Each participating site will maintain appropriate medical and research records for this trial, in compliance with ICH E6, ISO 14155:2011 and regulatory and institutional requirements for the protection of confidentiality of participants.

Source data are all information, original records of clinical findings, observations, or other activities in a clinical trial necessary for the reconstruction and evaluation of the trial. Examples of these original documents and data records include, but are not limited to, hospital records, clinical and office charts, laboratory notes, memoranda, participants' memory aids or evaluation checklists, pharmacy dispensing records, recorded audio tapes of counseling sessions, recorded data from automated instruments, copies or transcriptions certified after verification as being accurate and complete, microfiches, photographic negatives, microfilm or magnetic media, x-rays, and participant files and records kept at the pharmacy, at the laboratories, and medico-technical departments involved in the clinical trial. It is acceptable to use CRFs as source documents. For this protocol, responses to subject questionnaires and scales will be collected on two-part no carbon required (NCR) paper CRF pages. One copy will be collected by the sponsor with the remaining copy left at the investigation site.

It is not acceptable for the CRF to be the only record of a subject's participation in the study. This is to ensure that anyone who would access the patient medical record has adequate knowledge that the patient is participating in a clinical trial.

Source documents for this study will include:

- Digital photographs - will be kept in a password-protected file on the secure server at the investigation site. Only the PI and SI will have access to the digital files. Participants will sign a photograph waiver at the beginning of the study which will describe in detail how these photos may be used, such as web-based marketing purposes or academic publications.
- CRFs - will be in paper format. There will be one CRF for each participant in the study, which will be kept in a locked drawer at the investigation site. At the completion of the study, the CRFs will be scanned to pdf format and stored in a password-protected file on the secure server at the investigation site. After the paper forms are scanned and digitized, they will be shredded and properly disposed as sensitive medical records.

- Recorded data from Cutometer® - all data is electronically recorded and saved in a software program on the PI's password-protected desktop computer at the investigation site.
- Subject questionnaires - will be in paper format, then scanned to pdf format and stored in a password-protected file on the secure server at the investigation site. After the paper forms are scanned and digitized, they will be shredded and properly disposed as sensitive medical records.
- Rater data collection sheets - will be in paper format, then scanned to pdf format and stored in a password-protected file on the secure server at the investigation site. After the paper forms are scanned and digitized, they will be shredded and properly disposed as sensitive medical records.

12 QUALITY ASSURANCE AND QUALITY CONTROL

Quality control (QC) procedures will be implemented beginning with the data entry system and data QC checks that will be run on the database will be generated. Any missing data or data anomalies will be communicated to the site(s) for clarification/resolution.

Following written SOPs, the monitors will verify that the clinical trial is conducted and data are generated, documented (recorded), and reported in compliance with the protocol, GCP, and the applicable regulatory requirements.

The investigational site will provide direct access to all trial related sites, source data/documents, and reports for the purpose of monitoring and auditing by the sponsor, and inspection by local and regulatory authorities.

13 ETHICS/PROTECTION OF HUMAN SUBJECTS

13.1 ETHICAL STANDARD

The investigator will ensure that this study is conducted in full conformity with Regulations for the Protection of Human Subjects of Research codified in 45 CFR Part 46, 21 CFR Part 50, 21 CFR Part 56, and/or the ICH E6, ISO 14155:2011, the Declaration of Helsinki, Council for International Organizations of Medical Science (CIOMS), International Ethical Guidelines for Biomedical Research Involving Human Subjects (2002), or another country's ethical policy statement, whichever provides the most protection to human subjects.

13.2 INSTITUTIONAL REVIEW BOARD

The protocol, informed consent form(s), recruitment materials, and all participant materials will be submitted to the IRB for review and approval. Approval of both the protocol and the consent form must be obtained before any participant is enrolled. Any amendment to the protocol will require review and approval by the IRB before the changes are implemented to the study. All changes to the consent form will be IRB approved; a determination will be made regarding whether previously consented participants need to be re-consented.

13.3 INFORMED CONSENT PROCESS

13.3.1 CONSENT/ASSENT AND OTHER INFORMATIONAL DOCUMENTS PROVIDED TO PARTICIPANTS

Informed consent is required for all subjects in a study. In obtaining and documenting informed consent, the investigator should comply with applicable regulatory requirements and should adhere to 45 CFR Part 46, 21 CFR Part 50, 21 CFR Part 56), another country's ethical policy statement and/or ICH GCP. Prior to the beginning of a trial, the investigator should have the IRB's written approval for the protocol and the written informed consent forms(s) and any other written information to be provided to the participants. Consent forms describing in detail the study agent, study procedures, and risks are given to the participant and written documentation of informed consent is required prior to starting intervention/administering study product.

The following consent materials are submitted with this protocol:

- Consent to participate in study
- Photograph consent

13.3.2 CONSENT PROCEDURES AND DOCUMENTATION

Informed consent is a process that is initiated prior to the individual's agreeing to participate in the study and continues throughout the individual's study participation. Extensive discussion of risks and possible benefits of participation will be provided to the participants and their families. Consent forms will be IRB-approved and the participant will be asked to read and review the document. The investigator will explain the research study to the participant and answer any questions that may arise. All participants will receive a verbal explanation in terms suited to their comprehension of the purposes, procedures, and potential risks of the study and of their rights as research participants. Participants will have the opportunity to carefully review the written consent form and ask questions prior to signing. The participants should have the opportunity to discuss the study with their surrogates or think about it prior to agreeing to participate. The participant will sign the informed consent document prior to any procedures being done specifically for the study. The participants may withdraw consent at any time throughout the course of the trial. A copy of the informed consent document will be given to the participants for their records. The rights and welfare of the participants will be protected by emphasizing to them that the quality of their medical care will not be adversely affected if they decline to participate in this study.

